7.2.3 Sensitivity Analyses

In addition to primary analysis, a modified Main Analytical Approach in Section 7.2.2 will be applied for sensitivity analysis.

For Step 1: the two scenarios will be combined as one:

- If **CFB ≥ 0 or CFB < 0** , the CFB will be **set to Zero**.

Other steps are consistent with the Main Analytical Approach in Section 7.2.2.

7.2.4 Supplementary Analyses

The primary efficacy analysis described in section 7.2.2 will be repeated on the PPS and FAS.

7.2.5 Other Analyses

Percentage Change from Baseline

The percentage change of DYS measured by NRS from Baseline to Week 12 will be performed the same method as analysis of primary outcome in section 7.2.2.

Percentage change from Baseline = (the mean of Visit - the mean of Baseline) / the mean of Baseline)*100%.

The Visit refers to Week 12 measurement or other post-baseline visits.

E-diary Compliance

All subjects will be administered an e-Diary after adequate training at Visit 2. Subjects are required to record uterine bleeding and endometriosis-associated pain every day for the entire duration of the study (until end of study). The use of rescue medications for endometriosis-associated pain will also be recorded. Compliance to e-Diary filling will be summarized for treatment group using PAS including the following variables:

Planned e-Diary Duration (days) = Date of Last Study Visit – Date of Visit 2 +1.

If a subject completed or discontinued the study early, the date of last study visit will be the day of EOS. If a subject is still ongoing, the date of last visit will be replaced by the date of last e-Diary record or last visit date (if applicable), whichever comes last.

- Total days with e-Diary (days) is the total days during study with e-Diary data. All days with non-missing e-Diary regardless of correction or refilling will be included.
- Compliance to e-Diary (%) = (Total Days with e-Diary / Planned e-Diary Duration) × 100.

Based on above calculation formula of e-Diary compliance, another compliance (%) will be calculated to exclude those days with missing and corrected/refilled e-Diary from today days with e-Diary (days).

E-diary data will be listed on the PAS.

Receiver Operating Curve (ROC) Analysis for Determination of Thresholds for Reduction in Pain

The ROC analysis will contain all subjects who received at least one dose of IMP.

- Subjects who a) prematurely discontinue before Week 13, or b) either prematurely discontinue at or after Week 13 but are missing Week 13 PGIC will be assigned a PGIC response of "No change" (PGIC Non-responder).
- Observed values of DYS measured by NRS without any imputation will be used for ROC analysis.

The threshold for reduction in pain will be determined based on a ROC analysis using the PGIC assessment at Week 13 as an anchor and mean change of DYS measured by NRS from Baseline to Week 12 as the independent variable. The PGIC is a 7-point response scale: "Since I started taking the IMP, my endometriosis related pain has: very much improved (1), much improved (2), minimally improved (3), not changed (4), minimally worse (5), much worse (6), very much worse (7)." **The responses of "very much improved (1)" and "much improved (2)" on PGIC will be used to define PGIC responders**, and the threshold for response will be chosen to balance sensitivity and specificity. The threshold with maximum Youden's index (Youden's index=sensitivity + specificity – 1) will be selected as optimal threshold. Treatment group will be considered in ROC analysis. No other covariates will be included in the ROC analysis.

Empirical Cumulative Distribution Function (eCDF) Curve

In addition to the anchor-based method, the eCDF method will be used to determine the clinically meaningful improvement. The eCDF curves display a continuous view of the mean score change (both positive and negative) in DYS at Week 12 on the horizontal axis, with the vertical axis representing the cumulative proportion of patients experiencing up to that level of score change. An eCDF curve should be plotted for each distinct anchor category and treatment group.

Dose-Response Relationship

To study the dose-response relationship, the mean CFB to Week 12 measurement will be plotted versus nominal and log-transformed dosage (placebo, HMI-115 60mg, 120mg and 240mg). The dosage (0, 60, 120, 240) will be log-transformed using the function $\log(\text{dosage}+1)$, where \log represents the natural logarithm function. A simple linear regression model will be fitted as a function of dose to characterize the dose-response relationship. In case of lack-of-fit

of the simple linear regression model, multivariate or non-linear regression models may be explored.

The following SAS code will be used:

```
PROC REG data=data;
```

```
  MODEL cfb = log_dose / clb;
```

```
RUN;
```

```
PROC REG data=data;
```

```
  MODEL cfb = dose / clb;
```

```
RUN;
```

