7.2 Subject Withdrawal from the Study

The subject may withdraw or may be withdrawn from the study:

- If they decide to do so, at any time and irrespective of the reason
- At the specific request of the Sponsor

Subject discontinuation from IMP or withdrawal from the study should be avoided as much as possible. Every attempt should be made to restart IMP if medically appropriate and approved by Medical Monitor, irrespective of the duration of holding IMP.

In the event of withdrawn from the study during the treatment period, if possible, an early discontinuation visit (procedures same as Visit 9) needs to be performed as soon as possible and an on-site follow-up visit (procedures same as Visit 10) after 12 weeks from the last dose should be conducted. If the subject is unwilling to attend the on-site follow-up visit, a follow-up phone call should be attempted if the subject agrees, to collect safety information (monitoring AE, pregnancy status, concomitant medications) (refer to Section 1.3).

In the event of withdrawn from the study during the follow-up period, if possible, an on-site follow-up visit (procedures same as Visit 10) is recommended to complete as soon as possible followed by a phone call follow-up at 12 weeks from the last dose to collect safety information (monitoring AE, pregnancy status, concomitant medications). If the subject is unwilling to attend an on-site

Version 6.0 46 of 138 April 11, 2024

follow-up visit, a phone call follow-up at 12 weeks from the last dose should be attempted if the subject agrees (refer to Section 1.3).

If the subject withdraws informed consent for disclosure of future information, the Sponsor may retain and continue to use any data collected before such a withdrawal of consent.

Note: For subjects discontinued from IMP or withdrawn from study, no additional PK and ADA sampling except EOT and EOS visits (if possible) is required after IMP discontinuation.

Handling of subjects with suspected COVID-19 infection:

If a subject develops fever or symptoms suspected of being a result of COVID-19 during the study, they will be instructed to follow-up with their regular healthcare provider or follow the instructions for suspected COVID-19 cases per their local health authority.

A subject may be withdrawn by the Investigator based on discussion with the Sponsor and Medical Monitor under the following circumstance:

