8.1 Efficacy Assessments

8.1.1 Electronic-Diary (e-Diary)

All subjects will be administered an e-Diary after adequate training at Visit 2. Subjects are required to record uterine bleeding and endometriosis-associated pain every day at around the same time for the entire duration of the study. The use of rescue medications for endometriosis-associated pain will also be recorded. Compliance to e-Diary filling will be assessed as shown in the SoA (refer to Section 1.3). Subjects need to return the e-diary devices after the completion of study participation or after withdrawal from the study.

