2.1 General Considerations

- 'Baseline' is defined as the last available pre-treatment assessment (including unscheduled assessments) unless otherwise specified in the SAP.
- 'End of Study (EOS)' is defined as the last available post-treatment assessment.
- 'Study Day' will be calculated relative to the date of First Administration of IMP (i.e., prior to treatment, Study Day = Assessment Date -First Administration of IMP Date; otherwise, Study Day = Assessment Date - First Administration of IMP Date+1). The day of the first IMP administration will be Day 1. In case of partial or missing event date, study day will appear missing.
- Measurements collected at early discontinuation visit (EDV) will be mapped to the scheduled visit according to the analysis visit window in Table 12.2. If EDV measurement allocates to a visit without a scheduled measurement, EDV measurement will be considered for analysis by visit. If EDV measurement allocates to a visit with existing scheduled measurement, EDV measurement will not be considered for analysis by visit. Unscheduled visits will not be mapped to scheduled visits.
- For by-visit summaries, only scheduled assessments will be used in tables, and if there are repeated post-first dose assessments, only the earlier value will be used in summary. In the subject listing, data will be presented under the nominal visits.
- Continuous data will be summarized in terms of the number of observations (n), mean, standard deviation (SD), first quartile (Q1), median, third quartile (Q3), minimum and maximum, unless otherwise stated. The minimum and maximum will be reported to the same number of decimal places as the raw data recorded in the database. The mean, median, Q1 and Q3 will be reported to one more decimal place than the raw data recorded in the database. The SD will be reported to two more decimal places than the raw data recorded in the database. In general, the maximum number of decimal places reported shall be four for any summary statistic.
- Categorical data will be summarized in terms of frequency counts and percentages. Any planned collapsing of categories will be detailed in the SAP text and the data displays.

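### The e-Diary compliance denominator has no cut-off at study withdrawal, so perfect diary filling by a woman who withdraws during treatment and returns for the 12-week visit could score about 30–70%

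*SAP*

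**What the plan says.** SAP 7.2.5 (E-diary Compliance) defines the denominator as "Planned e-Diary Duration (days) = Date of Last Study Visit – Date of Visit 2 +1". Its end date for women who finish or leave early is set by "If a subject completed or discontinued the study early, the date of last study visit will be the day of EOS". The numerator is described as "Total days with e-Diary (days) is the total days during study with e-Diary data". A second percentage drops corrected or refilled days from the numerator and keeps the same denominator. Both are summarised by treatment group on the PAS. For women still ongoing, the end date may follow the last diary record; withdrawn women have no such rule.

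SAP 2.1 gives the meaning of EOS: "End of Study (EOS)' is defined as the last available post-treatment assessment".

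Protocol 8.1.1 covers the device: "Subjects need to return the e-diary devices after the completion of study participation or after withdrawal from the study". It names no day or visit for the return.

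Protocol 7.2 asks a woman who withdraws during treatment for a prompt early discontinuation visit and then, if possible, "an on-site follow-up visit (procedures same as Visit 10) after 12 weeks from the last dose should be conducted". If she declines: "If the subject is unwilling to attend the on-site follow-up visit, a follow-up phone call should be attempted if the subject agrees". For withdrawal in the follow-up period, "an on-site follow-up visit (procedures same as Visit 10) is recommended to complete as soon as possible", followed by a phone call. Under Protocol 7.1, a woman who only stops IMP stays in the study to Visit 10.

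**The concern.** Numerator and denominator can cover different periods. The numerator stops growing when a woman stops using the diary. The denominator runs on to whatever visit counts as EOS, which for a woman who withdraws during treatment can be a safety visit many weeks later. The ratio then mixes two things: how well she filled the diary while she was asked to, and the fact that she left.

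The table is reported by arm. If one arm loses more women during treatment and they return for the later visit, that arm looks less diligent with the diary even if every woman filled it daily until she left. The text also leaves room for two programmers to give the same woman very different values, depending on which date they take as the day of EOS.

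**Working it through.** The documents state no compliance percentage, so there is no figure to reproduce. The check applies the SAP formula to a woman who fills the diary every day until she withdraws.

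Inputs:
- S = days from Visit 2 to Day 1. The minimum is 35 (Protocol 4.1, SAP 1.1). Screening lasts at most 75 days, so S is at most 75, or 61 if Visit 1 to Visit 2 takes the full 14 days.
- L = study day of last dose: 1, 15, 29, 43, 57 or 71 (Protocol 1.3), ignoring visit windows.
- Later visit at L + 84 (12 weeks, Protocol 7.2), taken as exactly 84 days.
- W = study day of withdrawal. The documents do not give the lag from last dose; I assume 0, 7 or 14 days, from the two-week dosing interval.
- Assumed: she stops the diary or returns the device on day W, and the later visit is her EOS.

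Formulas, counting both end days:
- Diary days = S + W
- Planned duration = S + L + 84
- Compliance = (S + W) / (S + L + 84)
- Post-withdrawal days in the denominator = L + 84 − W

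The last quantity is 84, 77 or 70 days for a lag of 0, 7 or 14 days, that is 12, 11 or 10 weeks.

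Results for S = 35 and W = L + 7:

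| Last dose | Diary days | Planned days | Compliance |
|---|---|---|---|
| Day 1 | 43 | 120 | 35.8% |
| Day 15 | 57 | 134 | 42.5% |
| Day 29 | 71 | 148 | 48.0% |
| Day 43 | 85 | 162 | 52.5% |
| Day 57 | 99 | 176 | 56.25% |
| Day 71 | 113 | 190 | 59.5% |

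With the same 7-day lag, S = 61 gives 69/146 = 47.3% to 139/216 = 64.4%, and S = 75 gives 83/160 = 51.9% to 153/230 = 66.5%. Over the whole grid the lowest value is 36/120 = 30.0% (S = 35, last dose Day 1, withdrawal the same day). The highest is 160/230 = 69.6% (S = 75, last dose Day 71, withdrawal 14 days later).

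Other cases:
- She withdraws during treatment and the early discontinuation visit is her last assessment: about 100%.
- She withdraws in follow-up and the prompt on-site visit is EOS: about 100%. Only if the later phone call counted as an assessment would this change. With last dose on Day 71 the call falls on Day 71 + 84 = 155, so S = 35 and withdrawal on Day 113 give (35 + 113)/(35 + 155) = 148/190 = 77.9%.
- She only stops IMP: she stays to Visit 10 and keeps the diary, so there is no effect.
- The day of EOS is read as the withdrawal date: 100%.

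With the denominator cut at withdrawal, the ratio is (S + W)/(S + W) = 100% in every cell of the grid.

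**The case against.** The strongest case against is that this is an undefined end date in a descriptive table, not a demonstrated error. Protocol 8.1.1 fixes no return day. The 12-week visit follows Visit 10 procedures, which in the schedule of activities include the e-Diary compliance check, so she might still hold the device. For a woman who left early, the day of EOS could mean the day her participation ended, and SAP 7.3.1 uses EOS in yet another sense, for the Week 24 visit. All of this stands as a limit on certainty. It does not rescue the rule, because the only definition the SAP gives points to the later assessment.

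A second argument is that 100% for a woman who left after Day 15 would hide missing data. That would matter if the table measured completeness, but the SAP presents it as compliance with filling the diary.

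A reader might infer three stronger things that the documents do not support:
- *Any fully compliant withdrawn woman scores about 50%.* That is one mid-treatment scenario. The range is wide, and many withdrawn women are not affected.
- *Each arm mean is understated by 4 to 6 points.* This multiplies the plan's 10% discontinuation rate by the individual shortfall. Protocol 9.2 and SAP 1.4 use that 10% for women who leave without giving efficacy data. It does not estimate how many withdraw during treatment and return at 12 weeks.
- *Diary compliance is the only measure of how complete the primary data are.* SAP 7.2.2 summarises the dysmenorrhea score by arm and visit, SAP 2.1 requires n in such summaries, and SAP 3.1 reports withdrawals with reasons by arm.

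**Conclusion.** The point holds in a limited form. SAP 7.2.5 has no cut-off at study withdrawal, and its stated end date, taken with SAP 2.1, gives a misleading value to a woman who withdraws from the study during treatment and attends the 12-week visit. Her denominator then carries about 10 to 12 weeks after withdrawal. Perfect filling scores about 30–70%, and 48.0–52.5% with 35 screening days, last dose on Day 29 or 43 and withdrawal a week later.

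This rests on three assumptions: the later visit is her EOS, diary entries stop at withdrawal, and withdrawal comes within 14 days of the last dose. The size of any distortion between arms cannot be computed from the documents. No analysis set, imputation rule or efficacy test in the plan uses the compliance percentage, so the consequence is a possible misreading of the by-arm adherence summary. Priority is low, but the correction is easy.

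**What to change.** In SAP 7.2.5, for women who complete or leave the study, set:

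Planned e-Diary Duration = min(date of EOS visit, date of withdrawal from study) − date of Visit 2 + 1

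Where there is no study withdrawal, the EOS visit date applies alone. Count diary days within the same window, so that entries made after withdrawal cannot push the ratio above 100%. Use this denominator for both compliance percentages, and leave the rule for ongoing women as it is.

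The cost is one sentence in the SAP and a small programming change. It needs visit, withdrawal and diary dates. SAP 3.1 already plans a by-subject listing of withdrawal details, although the eCRF is not among the documents, so the withdrawal date field should be confirmed. Using the withdrawal date avoids needing a device-return date, which the documents do not mention collecting.

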7.1 Discontinuation of IMP

It may be necessary for a subject to permanently discontinue (definitive discontinuation) the IMP. If the IMP is definitively discontinued, the subject will remain in the study until Visit 10 to be evaluated for safety and efficacy of the IMP. Please refer to Section 10.4 and 8.4.5 for details on contraceptive guidance and collection of pregnancy information.

The Investigator or Medical Monitor (and, if needed, with DMC review) may temporarily hold or stop the dosing of IMP to a subject at any time during the study. For subjects that discontinue IMP for reasons related to safety, unblinding of the treatment assigned to the subject may be carried out if deemed necessary by the Sponsor to assess any potential safety signal or by the Investigator to provide adequate medical care to the subject. All details of reasons, therapies that may have been subsequently started should be well documented and reviewed.

Examples of conditions or symptoms that may warrant holding or stopping IMP at the Investigator's and/or Medical Monitor's discretion include:

- Occurrence of a severe or serious AE assessed as related to IMP
- Repeating premature ventricular contractions (PVC) confirmed by additional ECG examination at least 30 minutes apart, or QTcF interval >500 ms, or increase in QTcF interval >60 ms compared to baseline in absence of possible causes other than the IMP
- Significant decrease of neutrophils count < 1500 mm³ confirmed by repeat measurement

Version 6.0 45 of 138 April 11, 2024

- Pregnancy
- Intolerance of the IMP authorized under this protocol
- If in the Investigator's opinion, continuation with the administration of the IMP would be detrimental to the subject's well-being

Investigator must notify the Sponsor within one calendar day of being aware of an event that may warrant holding or stopping the IMP. If the IMP is held due to safety concerns, approval by the Medical Monitor is required prior to resumption of IMP. If the subject meets the holding or stopping conditions again after resumption (re-challenge), the IMP will be permanently discontinued.

Unless informed consent is withdrawn, subjects who permanently discontinue IMP during the treatment period should attend all subsequent visits up to Visit 10 and complete all procedures (except IMP administration related) as outlined in the SoA.

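### The ROC analysis for the DYS threshold assigns discontinuers a PGIC of No change beside their observed DYS change, and leaves open how treatment group enters, so some anchor labels can be false and the cut-off may differ by arm

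*SAP*

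**What the plan says.** The ROC part of SAP 7.2.5 sets these rules:

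- **Population.** "The ROC analysis will contain all subjects who received at least one dose of IMP".
- **Anchor.** Two groups are scored *No change*, which is a PGIC non-response. The criteria read "prematurely discontinue before Week 13, or b) either prematurely discontinue at or after Week 13 but". Limb (a), discontinuation before Week 13, applies whether or not a PGIC was recorded. Limb (b), later discontinuation, applies only where the Week 13 PGIC is missing; its closing words are "are missing Week 13 PGIC will be assigned a PGIC response of", followed by that category.
- **DYS.** "Observed values of DYS measured by NRS without any imputation will be used for ROC analysis".
- **Cut-off.** It is the maximum of Youden's index, and "the threshold for response will be chosen to balance sensitivity and specificity".
- **Treatment.** "Treatment group will be considered in ROC analysis. No other covariates will be included in the ROC analysis". The method is not given.

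Protocol 7.1 says that after permanent discontinuation of IMP "the subject will remain in the study until Visit 10 to be evaluated for safety and efficacy of the IMP", with all procedures other than dosing. The Schedule of Activities has PGIC at Visit 9 (Week 13). Protocol 9.4.3 uses this ROC analysis, together with the eCDF, to define a DYS responder. It mentions neither the reassignment nor treatment group.

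**The concern.** An anchor analysis relates two reports from the same woman: her global impression and her change in pain. PGIC is the reference standard here. Counting a discontinuer as a failure is a defensible convention when arms are compared. In a threshold analysis it can put a false label beside a true DYS change.

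Consider a woman who stopped IMP, stayed in the study, improved on DYS and answered *much improved* at Week 13. On one reading of the rule she enters the ROC as a non-responder with a large pain reduction. SAP 9.3, which analyses PGIC itself, has no such rule (it recodes only for rescue use), so the same answer can count as a response there.

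The second issue is treatment group. A responder definition needs one cut-off. If treatment is a covariate or a stratifier, the same DYS change could be a response in one arm and not in another. What is at stake is the threshold that Protocol 9.4.3 would carry forward.

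**Working it through.** **The plan's own figure.** The documents give no AUC, threshold or count of reassigned subjects for the ROC, so there is nothing to reproduce.

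**Inputs.** From the documents: SD of DYS change 2.0, 38 subjects per arm and 152 in total (SAP 1.4). Assumed: mean change -2, 40% true PGIC responders, correlation 0.6 or 0.7 between DYS change and the scale underlying PGIC, and 10% of subjects recoded. The 10% is illustrative. The dropout allowance in SAP 1.4 covers women without efficacy data, who could not enter the ROC anyway, so it does not measure the affected group.

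**How many labels are false.** 152 × 0.10 = 15.2 recoded. If 40% of them are true responders, 15.2 × 0.40 = 6.1 false labels. Women with PGIC 3 to 7 are non-responders either way.

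**Recoding unrelated to DYS.** The non-responder group grows from 0.60 to 0.60 + 0.40 × 0.10 = 0.64 of subjects. At correlation 0.7 (sensitivity 0.757, specificity 0.740, AUC 0.831):

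- New specificity = (0.60 × 0.740 + 0.04 × 0.243) / 0.64 = 0.709.
- New AUC = (0.60 × 0.831 + 0.04 × 0.5) / 0.64 = 0.810.
- New Youden index = (0.60 / 0.64) × old index at every cut-off, so the large-sample cut-off does not move.

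**Recoding related to DYS.** Large-sample simulation, with the odds of recoding multiplied by 2.7 per SD of DYS change:

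| Who is recoded (10%) | Correlation 0.6: specificity, AUC, cut-off | Correlation 0.7: specificity, AUC, cut-off |
|---|---|---|
| Nobody | 0.70, 0.78, -2.17 | 0.74, 0.83, -2.21 |
| Unrelated to DYS | 0.67, 0.76, -2.17 | 0.71, 0.81, -2.21 |
| More often those who improved more | 0.60, 0.72, -1.93 | 0.64, 0.76, -2.01 |
| More often those who improved less | 0.70, 0.79, -2.19 | 0.74, 0.84, -2.24 |

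The cut-off shifts by 0.24 or 0.20 in the third row and by about 0.03 in the fourth. Allowing for somewhat different strengths of dependence, a fair range is -0.08 to +0.01 for AUC and up to about 0.3 point for the cut-off. This is not a mathematical bound: odds multiplied by 7.4 per SD towards the best improvers gave shifts of 0.37 to 0.45.

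**A single trial.** With 38 per arm, correlation 0.6, assumed arm means of -1.5, -2.0, -2.5 and -2.9, and recoding unrelated to DYS, the pooled cut-off moved in 38% of simulated trials. It moved by more than 0.5 point in 15%, with a mean shift near zero.

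**Treatment group.** With the same arm means, treatment entered as a logistic covariate and the cut-off converted back to a DYS change per arm:

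- Equal 10% recoding: large-sample arm cut-offs are essentially equal (-2.30 to -2.35).
- Recoding of 5/10/15/20% by arm: -2.15, -2.28, -2.49 and -2.73, a spread of 2.73 - 2.15 = 0.58. With the true PGIC every arm is near -2.40.
- At 38 per arm the median gap between the highest and lowest arm cut-off is 1.3 points with the recoding and 1.2 without it, so most of it is sampling noise.

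Separate cut-offs are also imprecise. The SD of the Youden cut-off is about 0.83 with 34 subjects against about 0.55 with 136 at correlation 0.6, and about 0.73 against 0.47 at correlation 0.7.

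**The case against.** The strongest reply is that the rule concerns leaving the study, not stopping IMP. Limb (b) speaks of discontinuing at or after Week 13, but the last dose is at Week 11, so the verb there cannot mean IMP, and limb (a) uses the same verb. Elsewhere the SAP names IMP or study treatment when it means that (1.3.2.7, 7.2.1). On this reading an early discontinuation visit before Day 79 maps to an earlier visit (SAP 2.1 and Table 12.2). There is then usually no Week 13 PGIC to overwrite, and often no Week 12 DYS.

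Much of this stands, and a reader should not infer that the SAP certainly overwrites recorded answers. It does not settle the point. SAP 2.1 uses similar wording for women who stop during treatment and still supply follow-up data, which suits stopping IMP. On the study reading, the rule still supplies an invented anchor for any woman with an observed DYS change.

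Three further objections are right:

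- The words in "are missing Week 13 PGIC will be assigned a PGIC response of" belong to limb (b), which fills a missing value. Any overwriting comes from limb (a).
- Recoding need not lower AUC or specificity. AUC rises slightly if it falls mainly on women who improved less.
- "Treatment group will be considered in ROC analysis" does not establish arm-specific cut-offs. The SAP speaks of one optimal threshold, and a by-arm display would be harmless.

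Finally, the ROC sits under other analyses, no analysis in the SAP uses the resulting DYS threshold, and the eCDF is a second route to it.

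**Conclusion.** The point holds in a limited form. As written, the rule gives some women an anchor they did not report while keeping their reported DYS change. If discontinuation means IMP, recorded answers of *much improved* or *very much improved* can be replaced. If it means the study, values are invented where DYS exists. The harm is confined to women with true PGIC 1 or 2 and an observed Week 12 DYS, and the documents do not allow their number to be estimated.

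On the assumed values, the effect on AUC is between -0.08 and +0.01. The large-sample pooled cut-off moves by at most about 0.3 point unless recoding is strongly concentrated in the women who improved most. Arm-dependent cut-offs are a possibility left open by unspecified wording, not something the SAP prescribes.

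A reader might infer that the efficacy conclusions are at risk. They are not: the primary ANCOVA and the secondary analyses do not use this threshold. The case for acting is that Protocol 9.4.3 needs one sound responder definition and the change costs little.

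**What to change.** In the ROC part of SAP 7.2.5:

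1. Include subjects with a recorded Week 13 PGIC, used as answered, and an observed Week 12 DYS change, regardless of IMP status. Exclude subjects missing either.
2. Remove the *No change* assignment from the main ROC analysis, or keep it only as a sensitivity analysis. If it is kept, say whether discontinuation means IMP or study, and repair limb (b), whose *either* has no alternative.
3. Derive one cut-off from all arms pooled, without treatment group. Show by-arm ROC curves descriptively only.

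The cost is SAP wording and the loss of a few subjects from the ROC set. No data collection and no other analysis changes.
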